Study Protocol and Statistical Analysis Plan (SAP) — Frailty Evaluation Component

1. Administrative information

Study title (short): FRAGSALUD — educational programme for frail/pre-frail older adults.

ClinicalTrials.gov Identifier: NCT05610605.

Study period: Conducted March 2022 – September 2023; assessments at baseline, 6 months (end of intervention), and 12 months (6 months post-intervention).

Primary SAP scope: frailty phenotype (Fried criteria) — score, categorical status (robust / pre-frail / frail).

Document date: 24/09/2025

2. Background & rationale (frailty)

Frailty is a state of increased vulnerability to stressors reflecting reduced physiological reserve. The study tested whether a 6-month educational intervention changes frailty status and frailty score compared with usual care in community-dwelling older adults with at least one Fried criterion.

3. Objectives (frailty component)

Primary frailty objective: Evaluate the effect of the 6-month educational programme on the Fried frailty total score at 6 months (end of intervention) and at 12 months (6 months post-intervention), compared with control.

Secondary frailty objectives:

- Evaluate shifts in frailty categories (robust / pre-frail / frail) between baseline, 6 months and 12 months.

4. Study design (brief)

Multicentre, parallel-group randomised controlled trial; participants randomised to educational programme or control (usual care). Assessments at baseline, 6 months, and 12 months.

5. Population and eligibility

Inclusion: Community-dwelling adults aged ≥ 65 years with ≥ 1 Fried frailty criterion (pre-frail or frail).

Exclusion: Institutionalised individuals; robust participants (zero Fried criteria).

Final analysed sample: 199 participants (109 intervention, 90 control after attrition).

6. Frailty measurement (operational definition)

Frailty was operationalised using the Fried physical frailty phenotype, consisting of:

- Shrinking (unintentional weight loss ≥ 4.5 kg or $\geq 5\%$ in past year).
- Weakness (sex- and BMI-specific grip strength cut-offs).
- Poor endurance/exhaustion (self-reported ≥ 3 days in previous week).
- Slowness (4-m timed walk with sex- and height-specific cut-offs).
- Low physical activity (Minnesota Leisure Time Physical Activity Questionnaire).

Scoring: 0–5. Categories: robust = 0; pre-frail = 1–2; frail ≥ 3 .

7. Outcomes (frailty-specific)

Primary frailty outcome: Change in Fried total score from baseline to 6 months and 12 months.

Secondary frailty outcomes:

- Proportion of participants in each frailty category at each timepoint.

8. Sample size

Target ≥ 196 participants, based on effect size 0.5 SD, $\alpha = 0.05$, power = 80%, allowing for 15% dropout.

9. Randomisation and allocation

Computerised block randomisation ensuring balance between groups.

10. Blinding

Participants and intervention deliverers were not blinded. Outcome assessors and analysts were blinded where possible.

11. Data collection schedule

Baseline: Fried components.

6 months: repeat assessments.

12 months: repeat assessments.

12. Statistical Analysis Plan

Analysis populations: Intention-to-treat and per-protocol (sensitivity).

Primary analysis: Linear mixed-effects model with Fried score as dependent variable; fixed effects for group, time, and group \times time; random effect for participant; adjusted for age, sex, education.

Secondary analysis: Frailty category transitions using chi-square, logistic regression, or multinomial models.

Sensitivity analyses: per-protocol, alternative frailty scoring, responder definitions.

13. Reporting and tables/figures

Baseline frailty table by arm.

Adjusted change table with β (95% CI) and p-values.

Frailty category transitions figure.

14. Key frailty results

At 6 months, intervention group reduced Fried score by -0.60 vs -0.015 in controls ($\beta = -0.515$, $p = 0.007$).

At 12 months, $\beta = -0.714$, $p < 0.001$.

Frailty category improved in intervention group: increase in robust participants, reduction in frail participants.

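### Intention-to-treat is named but not defined, the only analysed sample is 199 people counted after losses, and no listed sensitivity analysis is stated to address missing Fried scores

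*Combined protocol and SAP*

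**What the plan says.** Section 12 (Statistical Analysis Plan) gives "Analysis populations: Intention-to-treat and per-protocol (sensitivity" and defines neither population. The main analysis is "Primary analysis: Linear mixed-effects model with Fried score as dependent variable", with a participant random effect. Neither the estimation method nor an assumption about missing data is stated. The further analyses are "Sensitivity analyses: per-protocol, alternative frailty scoring, responder definitions".

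Section 5 (Population and eligibility) reports "Final analysed sample: 199 participants (109 intervention, 90 control after attrition". No number randomised appears anywhere, overall or by arm.

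Section 8 (Sample size) sets its target "allowing for 15% dropout". Section 9 describes "Computerised block randomisation ensuring balance between groups" but gives no allocation ratio. Section 13 plans "Adjusted change table with β (95% CI) and p-values" and lists no table of numbers observed by arm and visit.

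Section 1 carries "Document date: 24/09/2025", about two years after the study period closed in September 2023, and section 14 already prints the results.

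**The concern.** A sample counted after losses is not, on its face, everyone randomised. If the 199 are only those who stayed, an estimate from them would be reported under an intention-to-treat label that it does not earn, and the reader has no denominator with which to check.

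The mixed model helps only in part. Fitted by likelihood, it allows for dropout under missing-at-random, provided that people with incomplete follow-up stay in the data. If leaving is related to the outcome beyond what the model conditions on, the estimate can move in either direction. Participants knew their arm (section 10), so reasons for leaving could plausibly differ between arms. Nothing listed in section 12 is stated to show how far the result would move. A per-protocol analysis usually removes people; it does not examine those who left.

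**Working it through.** **Inputs from the document.** Analysed: 109 + 90 = 199 (section 5). Dropout allowance: 15% (section 8), used below only as an assumed loss. At 6 months, beta = -0.515 with p = 0.007; at 12 months, beta = -0.714 with p < 0.001 (section 14). No interval or standard error (SE) is printed.

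**Assumptions.** Two-sided p-value, normal approximation, SE held fixed, and every leaver without a 6-month score. Allocation and loss are assumed throughout.

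**Step 1: margin at 6 months.** A two-sided p of 0.007 gives z = 2.697. SE = 0.515/2.697 = 0.191. The 95% interval is about -0.89 to -0.14, so the margin to non-significance is 0.515 - 1.96 × 0.191 = 0.141.

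**Step 2: loss compatible with 109 and 90.** If equal numbers were randomised, each arm had at least 109, so control loss is at least 1 - 90/109 = 17.4%. With 15% overall loss, 199/0.85 ≈ 234 were randomised, or 117 per arm. Loss is then 8/117 = 6.8% in intervention and 27/117 = 23.1% in control. Control loss below 17.4% needs unequal allocation. For example, 15% control loss means 90/0.85 ≈ 106 randomised to control, fewer than the 109 kept in intervention.

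**Step 3: shift that removes 6-month significance.** If leavers differ from prediction by d points, their arm's mean moves by d × (loss fraction). A lower Fried score is better.

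- Control leavers better, intervention leavers as predicted: d = 0.141/(control loss).
- Control leavers better and intervention leavers worse by the same d: d = 0.141/(control loss + intervention loss).

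| Randomised per arm (assumed, 1:1) | Intervention loss | Control loss | d, control only | d, both arms |
|---|---|---|---|---|
| 109 | 0% | 19/109 = 17.4% | 0.81 | 0.81 |
| 117 | 8/117 = 6.8% | 27/117 = 23.1% | 0.61 | 0.47 |
| 120 | 11/120 = 9.2% | 30/120 = 25.0% | 0.56 | 0.41 |
| 130 | 21/130 = 16.2% | 40/130 = 30.8% | 0.46 | 0.30 |

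With unequal allocation and 15% loss in each arm (about 128 and 106 randomised), d is 0.94 for control only and 0.141/0.30 = 0.47 for both arms.

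**Step 4: both directions, 117 per arm.** If control leavers did 0.6 better, beta = -0.515 + 0.6 × 0.231 = -0.38 (p about 0.049). If they did 0.6 worse, beta = -0.515 - 0.6 × 0.231 = -0.65. For scale, section 14 gives a 6-month change of -0.60 in intervention and -0.015 in control.

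**Step 5: 12 months.** p < 0.001 gives only a bound: z at least 3.291, SE at most 0.714/3.291 = 0.217, margin at least 0.714 - 1.96 × 0.217 = 0.289. Loss by visit is unknown, so the two visits cannot be ranked for robustness.

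**The case against.** The line in section 5 describes what happened and does not define an analysis population. Its wording about attrition may attach only to the 90 controls, and the 199 may be those with any follow-up. The stated mixed model can keep people with partial data, and section 12 does name intention-to-treat. The document is a short frailty component, and section 13 does not claim to list every table, so counts may be reported elsewhere. Responder definitions could include counting missing as non-response.

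Much of this stands, and it rules out three stronger readings that a reader might infer:

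- **That intention-to-treat was breached.** The text does not say who entered the model.
- **That control lost more people.** The gap of 19 shows this only if allocation was about 1:1, which section 9 does not state. Under simple 1:1 allocation, a 109/90 split is compatible with chance (binomial p = 0.20), although blocking should be tighter.
- **That the reported betas are wrong.** Nothing here shows this.

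The illustration also has limits. The score runs from 0 to 5 and entry requires at least 1, so large improvements may be impossible for many leavers. If some people left after the 6-month visit, the 6-month loss is smaller and the shift needed is larger.

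The objection does not supply a definition of intention-to-treat, a number randomised, or an analysis stated to address missing scores. Even a correct likelihood fit would not test missing-at-random.

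**Conclusion.** The point holds in a limited form and should be fixed. Intention-to-treat is undefined, the one sample given is counted after losses and cannot be checked against the number randomised, and no listed sensitivity analysis is stated to address missing scores despite the expected dropout.

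The size is illustrative. In the 1:1 case with 15% overall loss, the tipping shift at 6 months is about 0.61 points in control leavers alone, or 0.47 in opposite directions in both arms. Across the 1:1 cases shown it runs from 0.81 down to 0.46 (control only) or 0.30 (both arms). All of this rests on assumed allocation and loss and on a fixed SE.

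A reader might also infer that the 6-month result is robust, because control leavers alone would have to beat prediction by more than the whole intervention-arm change of 0.60 unless control loss exceeded 0.141/0.60 = 23.5%. The documents do not support that reassurance. It moves one arm only; 1:1 with 15% overall loss already sits almost at that threshold; and the -0.60 may itself come from retained participants.

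**What to change.** 1. Define intention-to-treat as all randomised participants in their assigned arm. Fit the stated mixed model by likelihood to that set, using every available Fried score and keeping people with baseline only or partial follow-up. If the 199 are only those retained, label the existing beta a retained-participant analysis.
2. Keep the per-protocol analysis and add a missing-not-at-random sensitivity analysis at 6 and 12 months. Delta-adjusted imputation, varied by arm and in both directions, is one option; reference-based imputation is another. Fix the range before the run, report the shift at which the conclusion changes, and label the analysis post hoc, because the document postdates the study and already prints the results.
3. Show numbers randomised and observed, by arm and visit, beside beta, so that real loss fractions replace the assumed ones above. If the 199 turn out to be everyone randomised or everyone with any score, this settles the labelling question.

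The cost is a re-run on data already held, plus wording. The estimate may move either way or its interval widen. The deltas cannot be tested from the data, and a post hoc analysis carries less weight than a prespecified one. Baseline-only participants keep the randomised set intact but say nothing about leavers' later scores, so step 1 does not replace step 2.

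### Does naming both 6 and 12 months as primary, with no rule linking them, raise the trial's 5% error rate to 8 to 10%?

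*Combined protocol and SAP*

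**What the plan says.** Section 3 states the primary objective as the effect on the "Fried frailty total score at 6 months (end of intervention) and at 12 months (6 months post-intervention), compared with control". Section 7 repeats the pair: "Primary frailty outcome: Change in Fried total score from baseline to 6 months and 12 months". Neither section ranks one visit above the other.

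Section 8 plans the size on one comparison: "Target ≥ 196 participants, based on effect size 0.5 SD", with alpha 0.05 and 80% power, "allowing for 15% dropout". Section 12 specifies a single linear mixed model with group, time, their interaction and a participant random effect. It names no primary contrast and no multiplicity procedure. Section 13 plans estimates with 95% confidence intervals and p-values. Section 14 then gives one result per visit. The 6-month entry begins "At 6 months, intervention group reduced Fried score by -0.60 vs -0.015 in controls" and carries p = 0.007; the 12-month entry carries p < 0.001.

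**The concern.** Two primary contrasts, one alpha and two separate p-values look like two chances of success at 0.05 each. A trial that may claim success on either visit has a family-wise error above the 5% it states, and nothing in section 12 rules that reading out. If both visits had to succeed instead, error would be controlled, but the 80% power in section 8 would describe one test and not the pair. Either way, the stated error rate or the stated power would not belong to the primary claim.

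**Working it through.** **Inputs.** From the plan: alpha 0.05, power 80%, effect 0.5 SD, dropout 15%, target 196 (section 8); 109 and 90 analysed (section 5); p = 0.007 and p < 0.001 (section 14). Assumed because not stated: two-sided tests, 1:1 allocation, and the correlation ρ between the two change-from-baseline contrasts. With complete data, a random-intercept model implies ρ = 0.5. A first-order autoregressive pattern with visit-to-visit correlation 0.3 to 0.9 implies ρ of 0.57 to 0.69.

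**1. The plan's own sample size.** n per arm = 2(1.960 + 0.842)²/0.5² = 62.8, so 63, or 126 in total. Allowing for dropout, 126/0.85 = 149. The stated 196 is not reproduced at 80% power. It matches 90% power: 85 per arm, 170 in total, and 170 × 1.15 = 195.5, so 196. This is a separate matter from alpha, but it bears on step 4.

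**2. Error rate if either visit suffices.** P(at least one rejection) = 1 − P(|Z₁| < 1.96, |Z₂| < 1.96), with (Z₁, Z₂) bivariate normal and neither effect real.

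| ρ | Either visit suffices |
|---|---|
| 0 | 9.75% |
| 0.5 | 9.07% |
| 0.7 | 8.35% |
| 0.8 | 7.81% |
| 0.9 | 7.04% |

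The rate crosses 8% at ρ of about 0.77. It cannot exceed 0.05 + 0.05 = 10% when each test holds its own level.

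**3. Error rate under other rules.** If both visits are required, P(both reject) = 0.10 − P(at least one). When neither effect is real this is 0.10 − 0.0907 = 0.93% at ρ = 0.5. It cannot exceed 5%, because each test alone is at 0.05. One joint test of the interaction at 0.05 holds 5% by construction. Testing each visit at 0.025 gives 4.65% at ρ = 0.5 and 4.94% at ρ = 0.

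**4. Power if both visits are required.** At exactly 80% per test, joint power is 64% at ρ = 0 (0.80²) and 73% at ρ = 0.8. The planned number gives more than 80% per test. 196 × 0.85 = 166.6, or 83.3 per arm. The noncentrality is 0.5/√(2/83.3) = 3.227, so power per test is Φ(3.227 − 1.960) = 89.7%. Joint power is then 80.5% at ρ = 0, 82.8% at 0.5 and 85.3% at 0.8. With 109 and 90 analysed, the noncentrality is 0.5/√(1/109 + 1/90) = 3.511, power per test is 94.0%, and joint power is 88.3% to 91.0% over the same range. These figures take 0.5 SD as the effect at both visits.

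**5. The reported results under each rule.**

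- Either visit at 0.05: met.
- Both visits at 0.05: met, since 0.007 and < 0.001 are both below 0.05.
- Bonferroni at 0.025 each: both met.
- Holm: smaller p < 0.001 against 0.025, larger p 0.007 against 0.05; both met.
- Joint test on 2 degrees of freedom: the Wald statistic is at least the larger squared z. For p < 0.001 that is above 3.29² = 10.83, so the joint p is below exp(−10.83/2) = 0.0045 (normal approximation); met.

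**The case for a change.** The best case for a change is that a combined protocol and SAP should say what counts as success. The word joining the two visits does not say it, the interaction term is not named as a joint test, and section 14 reports two separate p-values. One sentence adopting Holm would cost no participants or data. It needs no ordering of the visits, and it would tie the stated 5% to the primary claim. That the results happen to pass does not show that the design controlled its error.

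Most of this stands as a description of the gap. Had the trial not yet reported, the sentence would be worth asking for. Two parts do not stand. First, an error rate of 8 to 10% is not a property of this plan. It belongs to one reading, in which either visit suffices, and no section adopts that reading; alpha appears once, in the sample-size line. Second, the loss of power under a both-visits rule follows from the nominal 80% and not from the stated target, which supports roughly 80% or more jointly (step 4).

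Nor does the remedy deliver what it is meant to secure. The document is dated 24/09/2025, the study ended in September 2023, and the results are in the same document. A rule added now would have to be labelled post hoc.

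**Conclusion.** The plan leaves out a success rule for its two primary visits, and no change follows, because supplying one now gains nothing. On the least favourable reading the family-wise error is about 8 to 10% (9.1% at ρ = 0.5, less than 8% above about 0.77). On the both-visits or joint-test reading it is at most 5%. The reported p-values of 0.007 and below 0.001 meet every rule considered, so the primary conclusion does not depend on which reading was intended.

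This rests on two-sided tests, on a correlation that the documents do not give, and on the p-values as printed in section 14. It concerns multiplicity across the two visits only. It does not vouch for the model behind those p-values, nor does it explain why 196 fits 90% power better than the stated 80%.

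### At least two of the five Fried items rest on reports from unblinded participants, and the plan specifies no analysis that separates them from the measured items

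*Combined protocol and SAP*

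**What the plan says.** Section 10 (Blinding) states that "Participants and intervention deliverers were not blinded", and then that "Outcome assessors and analysts were blinded where possible".

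Section 6 defines the five items, each worth one point on a 0–5 scale:

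- Measured by a performance test: "Weakness (sex- and BMI-specific grip strength cut-offs") and "Slowness (4-m timed walk with sex- and height-specific cut-offs").
- Reported by the participant: "Poor endurance/exhaustion (self-reported ≥ 3 days in previous week") and "Low physical activity (Minnesota Leisure Time Physical Activity Questionnaire").
- Mixed or unclear: "Shrinking (unintentional weight loss" above a threshold in the past year). No method of ascertainment is given.

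Section 7 makes the change in the total of these items the primary outcome. Section 12 lists "Sensitivity analyses: per-protocol, alternative frailty scoring, responder definitions" and defines none of the three. Section 11 has the Fried components recorded at baseline and the assessments repeated at 6 and 12 months. Section 13 lists a baseline frailty table, an adjusted change table and a transitions figure, but no follow-up table by item. Section 14 gives results for the total and the categories only.

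**The concern.** The trial compares an educational programme with usual care, and participants know which they received. That knowledge can influence how a person answers questions about tiredness and leisure activity. A blinded assessor who records the answer does not remove the influence, because it acts on the participant.

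The primary score adds such answers to two performance tests with equal weight. A fall in the total could come from better strength and speed, from a real change in activity or exhaustion, from a change in reporting, or from a mixture. The plan can be followed in full without showing which: any rescoring would satisfy the alternative-scoring item in Section 12, including one that keeps every reported item.

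What is at stake is interpretation. The construct is a physical frailty phenotype, and a reader of Section 14 cannot tell whether the measured components changed at all.

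**Working it through.** **Inputs.** From Section 14: 6-month changes of -0.60 and -0.015, β = -0.515 with p = 0.007; 12-month β = -0.714 with p < 0.001. From Section 6: five items of one point each. The documents give no item-level data.

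**1. The plan's own figure.** The unadjusted difference in change at 6 months is -0.60 - (-0.015) = -0.585. The reported β of -0.515 is adjusted for age, sex and education, so it cannot be reproduced without participant data. The steps below take it as given.

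**2. How many items are reported.** Two are clearly so. Weight loss makes a third if it was obtained by recall, or in part through the judgement of intent. The range is therefore k = 2 to 3.

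**3. Net shift per item that would produce the whole effect, |β|/k.**

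- 6 months: 0.515/3 = 0.172 and 0.515/2 = 0.258, or about 17 to 26 percentage points.
- 12 months: 0.714/3 = 0.238 and 0.714/2 = 0.357, or about 24 to 36 percentage points.

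**4. What that means as a share of positive answers.** Suppose that only the intervention arm misreports, that no new positives arise, and that the mean number of positive reported items at baseline is M. The share of positive answers that must flip is |β|/M. M is not in the documents; 0.5 to 2.0 is an assumed range, and 2.0 is the maximum if only two items are reported.

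| M (assumed) | 6 months, 0.515/M | 12 months, 0.714/M |
|---|---|---|
| 0.5 | 103% (impossible) | 143% (impossible) |
| 0.75 | 69% | 95% |
| 1.0 | 52% | 71% |
| 1.5 | 34% | 48% |
| 2.0 | 26% | 36% |

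The answer runs from impossible to about a quarter of answers at 6 months, depending on a quantity that is not reported.

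**5. Bias that would bring the result to p = 0.05** (normal approximation, SE taken as unchanged by the bias).

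- 6 months: p = 0.007 gives z = 2.697, so SE = 0.515/2.697 = 0.191. The 95% CI is -0.515 ± 1.96 × 0.191, about -0.89 to -0.14. The margin is 0.14 points in total: 0.047 per item over three items, or 0.070 over two.
- 12 months: p < 0.001 means z above 3.291, so SE is below 0.714/3.291 = 0.217. The margin exceeds 0.714 - 1.96 × 0.217 = 0.29 points: more than 0.096 per item over three, or 0.144 over two.

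**The case against.** The case for the plan has four parts.

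- **Only exhaustion carries the label self-reported.** Activity is by questionnaire, which makes two. The grip cut-offs depend on BMI, so weight was needed in some form, and weighing at visits fits the text as well as recall does. This stands: the documents do not establish that three of the five items are self-reported. Weight loss can be counted only for the judgement of intent, with its ascertainment unknown.
- **The undefined alternative scoring might include a performance-only score.** This also stands. The supportable statement is that no such analysis is specified, not that none exists.
- **Section 14 reports the score and the categories and claims nothing about measured function.** True, and it limits the criticism to interpretation. It does not remove the question of what the total reflects.
- **Separating the items would not settle the matter.** Grip and walk tests depend on the effort of the same unblinded participants, and a real gain in activity would show on the questionnaire. Both points are right. The separation would reduce the ambiguity without eliminating it.

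A reader might go further and infer that response bias alone explains the reported effect. The documents do not support that. Dividing β by the number of reported items shows only that the effect fits within the score range; the table of assumed M shows that plausibility turns on data not given.

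**Conclusion.** The point holds as a gap in the plan. At least two of five items in the primary score, and the judgement of intent in a third, depend on participants who know their arm. Assessor blinding does not protect those answers, and no specified analysis separates them from grip and walk. The part that response bias plays in the reported effect cannot be assessed from what is planned or reported.

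The 6-month result is the more sensitive: a small differential, about 0.14 points across the whole score, would bring it to p = 0.05. The 12-month result is sturdier, with a margin above about 0.29 points. These margins rest on the normal approximation and on an SE derived from the reported p-value. They show how much bias would matter; they are not evidence that bias of that size occurred.

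The primary analysis can stand. This is an inexpensive improvement to its interpretation.

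**What to change.** - **Section 12:** define the alternative scoring to include the primary mixed model fitted to a weakness-plus-slowness score (0–2), and to grip strength and 4-m walk time as continuous outcomes, at 6 and 12 months.
- **Section 13:** add a table of all five items by arm and visit. Showing all five prevents a rescoring from being chosen to suit the result.
- **Section 14:** report the measured-item estimates with 95% CIs beside the total-score result, and state that the total includes items reported by unblinded participants.
- **Labelling:** mark all of this as post hoc, because Section 14 already reports results.

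Do not make the claim conditional on the measured items moving in the same direction. With no true effect, a single measured outcome moves the favourable way about half the time, and a change confined to the reported items would not prove bias.

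The cost is a few model runs and one table, provided that item-level data and the underlying grip and walk values were kept at each visit, as Section 11 suggests. The 0–2 score is coarser and less powerful than the total, so a wide interval on it should not be read as absence of effect. The conclusion may become narrower.

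### The primary mixed model and the listed sensitivity analyses do not condition on baseline Fried score, so the 6- and 12-month contrasts are less precise than the collected data allow

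*Combined protocol and SAP*

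**What the plan says.** The primary outcome in section 7 is "Change in Fried total score from baseline to 6 months and 12 months". Section 12 analyses it with a "Linear mixed-effects model with Fried score as dependent variable; fixed effects for group, time, and group" × time, and completes the model with a "random effect for participant; adjusted for age, sex, education". The rest of the analysis list for the score is "Sensitivity analyses: per-protocol, alternative frailty scoring, responder definitions". The secondary analysis concerns frailty categories, not the score contrast.

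The baseline score is available: section 11 lists "Baseline: Fried components", and section 13 promises a "Baseline frailty table by arm". Section 9 gives the allocation method as "Computerised block randomisation ensuring balance between groups" and names no stratification factor. Section 5 reports an analysed sample of "199 participants (109 intervention, 90 control after attrition").

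The documents do not say whether baseline is one of the levels of time. They give no SD and no correlation between visits.

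**The concern.** Baseline score is usually among the strongest predictors of a later score on the same scale. A participant random effect may look as if it takes care of this, but it does not. With a free group term and baseline as a visit, the model uses baseline only by subtracting it in full, whatever the correlation. With follow-up visits alone, it does not use baseline at all. Either way the interval around the treatment effect is wider than it need be, at both time points.

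Section 9 leaves balance in Fried score to chance. The section 13 baseline table would show any difference between arms, but it would not supply an effect estimate adjusted for it. At stake is the precision of the primary contrast, not its validity.

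**Working it through.** **Inputs.** From the documents: 109 and 90 participants (section 5); the model terms (section 12); arm changes of -0.60 and -0.015, with β = -0.515 and p = 0.007 at 6 months (section 14). Assumed: r, the baseline to follow-up correlation, taken as 0.3, 0.5 and 0.7, and equal SDs unless stated.

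**Reading 1: baseline is a level of time, visits complete.** Let D be the observed baseline difference and F the follow-up difference between arms.

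- Planned contrast: F − D. Baseline-adjusted contrast: F − rD. The planned one differs by −(1−r)D.
- Per-arm variance in units of SD²: planned 2(1−r), adjusted 1−r². The identity 2(1−r) = (1−r²) + (1−r)² shows that the chance-imbalance term is the whole of the extra variance, not a second harm on top of it.
- SE ratio, planned to adjusted: √[2(1−r)/(1−r²)] = √[2/(1+r)].
- Number of people in an adjusted analysis who carry the same information as 199 in the planned one: 199(1+r)/2.

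**Reading 2: only the 6- and 12-month scores are modelled.** The per-arm variance is 1 unadjusted and 1−r² adjusted, so the SE ratio is 1/√(1−r²).

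| r | Reading 1: SE ratio | Reading 1: equivalent n of 199 | Reading 2: adjusted/planned variance | Reading 2: SE ratio |
|---|---|---|---|---|
| 0.3 | √(2/1.3) = 1.24 | 129 | 0.91 | 1.05 |
| 0.5 | √(2/1.5) = 1.15 | 149 | 0.75 | 1.15 |
| 0.7 | √(2/1.7) = 1.08 | 169 | 0.51 | 1.40 |

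**Unequal SDs under reading 1.** Eligibility cuts baseline scores at 1 or more, so the SDs may differ. With baseline SD s₀ and follow-up SD s₁, planned minus adjusted variance is (s₀² + s₁² − 2r·s₀s₁) − s₁²(1−r²) = (s₀ − r·s₁)². This is zero only when r·s₁/s₀, the slope of follow-up on baseline, equals 1.

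**Simulation check of reading 1.** Trials of 109 and 90 with three complete visits, SD 1 and a random intercept were simulated, 150 at each r. The planned 6-month contrast equalled the raw difference in mean change to rounding error (largest gap 1e-14), although a participant-level covariate was in the model. Mean SEs for the planned model and a common-baseline model were 0.168 and 0.136 (r = 0.3), 0.142 and 0.123 (0.5), and 0.110 and 0.102 (0.7). These agree with the formula.

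**Section 14 figures.** The arm changes differ by -0.60 − (-0.015) = -0.585, against β = -0.515, a gap of 0.070. By the check above, main effects of age, sex and education cannot produce this gap in the stated model with complete visits. Missing visits, different participants or a different fitted model could.

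**The case against.** The strongest reply is that nothing is wrong with the planned model. A free group × time mixed model is a standard choice, matches an outcome defined as change from baseline, and under reading 1 already uses the baseline scores. Both reported contrasts are significant, and an analysis added now cannot become confirmatory. All of this stands. It limits the point to a recommended improvement, and the primary interval keeps its width. It does not remove the point, because the score is in hand and one further model would use it fully.

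A second reply is that the loss may be small. That also stands: under reading 1 it is 8% at r = 0.7 with equal SDs and vanishes at a slope of 1. The documents cannot settle its size.

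It is tempting to settle it from section 14. On a normal approximation, two-sided p = 0.007 gives z = 2.697 and an SE of 0.515/2.697 = 0.191. From there one could compute adjusted SEs, or the baseline imbalance that would overturn significance. All such figures assume that 0.191 comes from the planned model on complete visits, and the gap between -0.585 and -0.515 puts that in doubt. On the same premise the SD of change is 0.191/√(1/109 + 1/90) = 1.34, so r = 0.7 with equal SDs needs an SD of 1.34/√0.6 = 1.73. That is implausible for baseline scores confined to 1 to 5, where even a uniform spread has an SD of 1.41. No such figures are offered here.

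**Conclusion.** The point holds as a loss of precision. No listed analysis of the Fried score conditions on its baseline value. If baseline is a modelled visit with complete data, the SE is about 24%, 15% or 8% larger than it need be at r = 0.3, 0.5 or 0.7, with equal SDs and assumed correlations. If baseline is not modelled, the adjusted variance would be 1−r² of the planned one.

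A reader might infer more, but the documents do not support it:

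- **Bias.** Under randomisation the planned contrast is unbiased in expectation.
- **An actual baseline imbalance.** The 109 and 90 are numbers of participants, and no baseline score by arm is given. An imbalance in one direction would make the planned model overstate benefit, and in the other understate it.
- **Conclusions that would change.** Nothing shows that either the 6-month or the 12-month result would.
- **The -0.585 versus -0.515 gap as proof of the omission.** It is a separate reporting question about which model and participants lie behind each figure.

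**What to change.** Add to section 12 a repeated-measures model of the 6- and 12-month Fried scores with group × visit, baseline Fried score × visit, age, sex and education. Because results are known, date it, label it a post-results sensitivity analysis, and show it beside the original model at both time points. State also whether baseline is a level of time in the original model.

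A model with a common baseline mean and unstructured covariance is an equivalent choice when follow-up is complete. In a simulated check on 109 and 90 completers it matched the baseline-adjusted model, and adding 40 dropouts with baseline only did not change it. Under a random-intercept covariance, or with intermittent missing visits, the two can differ, so the choice should be specified.

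The cost is a few lines of text and one extra analysis with two extra parameters, on data already collected. It cannot replace the original as confirmatory, and may move β in either direction.

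As a separate reporting item, state in section 14 whether -0.60 and -0.015 are raw or adjusted, and which participants and model produced them and β = -0.515, so that the -0.585 difference can be reconciled.
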